17.2.1.5. Progression-free survival (PFS)

PFS (months) is defined as (date of the first documented disease progression or death due to any cause, whichever occurs first – start date of treatment + 1)/30.4375.

The following censoring rules will be applied:

Situation	Date of Progression or Censoring	Outcome
No baseline and/or no post baseline assessment	Date of first dose	Censored
Disease progression documented between scheduled visits	Date of disease progression	PFS event
Death due to COVID-19	Date of last adequate assessment	Censored
Death before first assessment	Date of death	PFS event
Death between adequate assessment visits	Date of death	PFS event
New systemic therapy started prior to disease progression	Date of last adequate assessment* prior to the start of subsequent antineoplastic therapy	Censored
Treatment discontinuation for undocumented disease progression after the last adequate assessment	Date of last adequate assessment	Censored
No documented disease progression or death	Date of last adequate assessment	Censored

For patients in cohort 4, not evaluable by RECIST so being assessed by CA-125 criteria, the below table describes the criteria for defining progression and the date to be used in PFS derivation.

GCIG-Rustin-modified definition of progressive disease according to CA-125 definition		
	Definition of progression	Date of progression
Patients with elevated CA-125 before treatment and normalisation of CA-125 during treatment	CA-125 \geq 2 X ULN documented on 2 occasions**	Date CA-125 is first elevated to \geq 2 X ULN
Patients with elevated CA-125 pre-treatment that never normalises	CA-125 \geq 2 X nadir value on 2 occasions**	Date CA-125 is first elevated to \geq 2 X nadir value

Document: T:\sas\Debiopharm\Debio_1143\CZA60507\Biostatistics\Documentation\SAP\SAP Text\5
 Author: [REDACTED] Version Number: 5.0
 Version Date: 19APR2022

Template No.: CS_TP_BS016 Revision 5 Reference: CS_WI_BS005
 Effective Date: 01Apr2018

Copyright © 2009, 2010, 2012, 2016, 2018 IQVIA. All rights reserved. The contents of this document are confidential and proprietary to IQVIA Holdings Inc. and its subsidiaries. Unauthorized use, disclosure or reproduction is strictly prohibited.

Patients with CA-125 in normal range pre-treatment	CA-125 ≥ 2 X ULN documented on 2 occasions**	Date CA-125 is first elevated to ≥ 2 X ULN
----------------------------------------------------	---------------------------------------------------	-------------------------------------------------

**Repeat CA-125 anytime but normally not less than 1 week after the first elevated CA-125 level. CA-125 levels in samples obtained after administration of mouse antibodies or within 4 weeks after surgery or paracentesis should not be considered.

In patients for whom response to treatment is evaluated by both RECIST and CA-125 criteria, the RECIST evaluation will be used.

The median PFS and the PFS rate at each months will be derived from the Kaplan-Meier curves, as described in section 7.6.

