- **Disease control** is derived as any CR, PR or stable disease reported during the study
- **Duration of response** is the time from documentation of tumor response to disease progression, start of a systemic new anti-cancer therapy or analysis cut-off, whichever occurs first.
- **PFS duration** is defined as the time elapsed between treatment initiation and tumor progression or death from any cause, whichever occurs first. Censoring to the last assessment will be applied in the following situations: a) lost to follow-up, b) no progression before analysis cut-off, c) start of a new systemic anti-cancer therapy. The median PFS and the PFS rate at 6, 12 and 18 months will be derived from the Kaplan-Meier curves.
- **OS** is defined as the time elapsed between treatment initiation and death from any cause. In the main analysis, censoring to the last assessment will be applied in the following situations: a) lost to follow-up, b) alive at analysis cut-off. A sensitivity analysis will be performed by censoring the OS at the time of start of a new systemic anti-cancer therapy. The median OS and the OS rate at 12 months will be derived from the Kaplan-Meier curves.

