##### Definition of PFS and duration of response by CA-125

PFS based on CA-125 will be defined as the time from first study drug infusion until the GCIG-Rustin-modified criteria of progression are met, or until the date of death (with or without disease progression). Duration of CA-125 response will be defined as the time between when the CA-125 was first documented to have decreased by 50% in a patient who meets all the GCIG-Rustin-modified criteria for a CA-125 response, and the time the CA-125 is first documented to have risen to the point where the patient meets GCIG criteria of disease progression.

GCIG-Rustin-modified definition of progressive disease according to CA-125 criteria		
	Definition of progression	Date of progression
Patients with elevated CA-125 before treatment and normalization of CA-125 during treatment	CA-125 $\geq$ 2 X ULN documented on 2 occasions**	Date CA-125 is first elevated to $\geq$ 2 X ULN
Patients with elevated CA-125 pretreatment that never normalizes	CA-125 $\geq$ 2 X nadir value on 2 occasions**	Date CA-125 is first elevated to $\geq$ 2 X nadir value
Patients with CA-125 in normal range pretreatment	CA-125 $\geq$ 2 X ULN documented on 2 occasions**	Date CA-125 is first elevated to $\geq$ 2 X ULN

\*\*Repeat CA-125 anytime but normally not less than 1 week after the first elevated CA-125 level. CA-125 levels in samples obtained after administration of mouse antibodies or within 4 weeks after surgery or paracentesis should not be taken into account.

In patients for whom response to treatment is evaluated by both RECIST and CA-125 criteria, the date of response and progression will be the earliest date of the two methods.

¶Adapted from Rustin et al, 2004 (41)

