17.2.4. SENSITIVITY ANALYSIS OF SECONDARY EFFICACY VARIABLES

A sensitivity analysis will be performed by censoring the OS at the time of start of a new systemic anti-cancer therapy.

Another sensitivity analysis will be performed by censoring the OS at the time of death due to COVID-19, if applicable

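### The SAP counts death from any cause as a PFS event, then censors COVID-19 deaths in its only PFS analysis, unlike the protocol and its own OS and DoR rules

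*SAP*

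**What the plan says.** The SAP's definition line in 17.2.1.5 runs PFS from treatment start to the "date of the first documented disease progression or death due to any cause, whichever occurs first". The table that follows is introduced by "The following censoring rules will be applied" and is not labelled as a sensitivity analysis. Its row "Death due to COVID-19" gives the date of the last adequate assessment and the outcome censored.

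Protocol 11.4.1.1 ends PFS at "tumor progression or death from any cause, whichever occurs first" and names three censoring situations: "a) lost to follow-up, b) no progression before analysis cut-off, c) start of a new systemic anti-cancer therapy". Protocol Appendix C, for PFS by CA-125, also ends PFS at death, whether or not the disease has progressed.

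For OS, SAP 17.2.1.7 counts every death. SAP 17.2.4 then states: "Another sensitivity analysis will be performed by censoring the OS at the time of death due to COVID-19, if applicable". Duration of response (DoR) in SAP 17.2.1.6 counts death from any cause and makes no COVID-19 exception.

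SAP 4.3 lists three COVID-19 changes from the protocol: the treatment-failure definition, Category 7 of the efficacy set, and the OS sensitivity analysis. The PFS row is not among them. It is recorded only in the modification history, under version 3.0.

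**The concern.** A patient who dies of COVID-19 without progression has reached the end of progression-free survival as both documents define it. The censoring row removes that known event. It also moves the patient's time back to the last scan and lets the remaining patients stand in for what would have happened next. The resulting curve describes something other than the stated endpoint, and no companion analysis shows the difference.

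The three time-to-event endpoints also stop agreeing on what a death is. A responder who dies of COVID-19 without progression has an OS event and a DoR event but no PFS event. Someone who checks SAP 4.3 for departures from the protocol would not find this one, although it changes a main analysis and the listed OS item changes only a sensitivity analysis.

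**Working it through.** The documents give no sample size, event count or power for PFS, so there is no planned figure to reproduce. The check sets the rules side by side and then sizes the effect under stated assumptions.

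**Rules for a COVID-19 death before progression**

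| Endpoint | Source | Main analysis | Sensitivity analysis |
|---|---|---|---|
| PFS | Protocol 11.4.1.1 | Event | None |
| PFS | SAP 17.2.1.5, definition | Event | None |
| PFS | SAP 17.2.1.5, table | Censored at last adequate assessment | None |
| DoR | SAP 17.2.1.6 | Event | None |
| OS | SAP 17.2.1.7, 17.2.4 | Event | Censored |

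The second and third rows conflict within one SAP section. The third row also conflicts with the protocol and stands alone against DoR and OS.

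**Overlapping rows.** A COVID-19 death before any post-baseline scan fits three rows of the PFS table: no post-baseline assessment (censored at first dose), COVID-19 death (censored at last adequate assessment) and death before the first assessment (event). A later COVID-19 death also fits the row for deaths between adequate assessments (event). No order of precedence is given. The section has no rule for attributing a death to COVID-19; the eCRF-based rule in SAP 6.5 concerns treatment failure only.

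**Share of a cohort.** One patient is 1/8 = 12.5%, 1/11 = 9.1% or 1/15 = 6.7%. Futility stops recruitment at 8 or 11 evaluable patients, and SAP 4.3 refers to the futility of the Part B cohorts, so the larger shares look the more relevant. These are shares of patients, not effects on a median or rate.

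**Effect on the Kaplan-Meier curve.** Let n be the number at risk just after the patient's last scan, including that patient. Let m others progress before the death, with nobody else censored in between. Relative to its level at that scan, the curve just after the death is:

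- death counted: (n − m)/n × (n − m − 1)/(n − m) = (n − m − 1)/n
- death censored at the scan: (n − 1 − m)/(n − 1)

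The ratio is n/(n − 1), so censoring raises the curve by that factor from the death onward. Between the scan and the death the censored curve can sit slightly lower, because the patient has already left the risk set.

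**Worked example (assumed data).** Eight patients: progression at 1.84 months (three), 3.68 (two), 5.52 and 7.36, and one COVID-19 death at 3.0 months with the last scan at 1.84. The 8-weekly scan interval is 56/30.4375 = 1.84 months.

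- Death counted: 5/8 = 62.5% after 1.84; × 4/5 = 50.0% after 3.0; × 2/4 = 25.0% after 3.68; × 1/2 = 12.5% after 5.52.
- Death censored: 5/8 = 62.5% after 1.84 and still 62.5% after 3.0; × 2/4 = 31.25% after 3.68; × 1/2 = 15.6% after 5.52.

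Six-month PFS moves from 12.5% to 15.6%, a factor of 5/4 as the formula gives. The median, taken as the first time the curve is at or below 50%, moves from 3.0 to 3.68 months.

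**Average effect (simulation).** Assumptions: exponential PFS with the stated true median; one or two COVID-19 deaths, each at a uniformly distributed time before that patient's progression; censoring at the last 8-weekly scan, or at day one if there was none; all other patients followed to progression; 1,500 cohorts per setting. Differences are censored minus counted.

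| Patients | True median (months) | COVID-19 deaths | 6-month PFS (points) | Median (months) |
|---|---|---|---|---|
| 8 | 2 | 1 | +2.1 | +0.55 |
| 8 | 2 | 2 | +4.5 | +0.74 |
| 8 | 4 | 1 | +4.6 | +1.12 |
| 8 | 4 | 2 | +9.6 | +1.98 |
| 15 | 2 | 1 | +1.0 | +0.06 |
| 15 | 2 | 2 | +2.2 | +0.27 |
| 15 | 4 | 1 | +2.4 | +0.23 |
| 15 | 4 | 2 | +5.0 | +0.59 |

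**The case against.** The rule was deliberate and not concealed. The modification history records it under version 3.0, and Protocol 11.6 leaves the definitive analysis to the SAP. How to treat pandemic deaths is a choice of target: if the aim were PFS in the absence of COVID-19 deaths, and those deaths were unrelated to the tumour's course, censoring would be coherent and not biased upward for that aim. The SAP also sets COVID-19 events aside in its efficacy set.

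The stakes are modest. PFS is a secondary, descriptive endpoint; the primary endpoint is confirmed response, and no futility or efficacy boundary uses PFS. In the efficacy set, a patient lost to COVID-19 before any post-baseline scan is not a treatment failure and is excluded, so the row acts there mainly on later deaths. Earlier ones enter PFS only in the ITT set. PFS and OS events would not nest perfectly without this row either, because PFS is already censored at new systemic therapy while OS continues. Finally, changing a main rule this late in an open-label trial is itself uncomfortable.

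Most of this stands as context, and the nesting point takes away any argument that the row alone makes PFS and OS non-comparable. None of it removes the conflict. The any-cause definition is still in the SAP, no other target is stated or justified, and upward is the right direction relative to the endpoint as written. Counting these deaths restores the protocol's definition; it does not introduce a new one.

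**Conclusion.** The point holds. SAP 17.2.1.5 contradicts its own definition, departs from the protocol's PFS definition and censoring list, and treats COVID-19 deaths differently from OS and DoR. It offers no PFS analysis that counts them and does not list the change in 4.3.

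The size depends on the number of COVID-19 deaths before progression, which the documents do not give. With none, nothing changes. With one or two, and under the simulation assumptions above, 6-month PFS is higher on average by 2.1 to 9.6 points with 8 patients and by 1.0 to 5.0 points with 15. The median is longer by about 0.6 to 2.0 months and 0.1 to 0.6 months respectively. The primary response analysis and the stopping boundaries are unaffected. It should be corrected, but it does not bear on the trial's main decision.

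**What to change.** In the SAP 17.2.1.5 table, make a COVID-19 death an event at the date of death, or delete the row so that the other death rows apply. In 17.2.4, add a PFS sensitivity analysis that censors COVID-19 deaths at the last adequate assessment, to be run if at least one occurs, as for OS. There, state how a death is attributed to COVID-19 and that this rule takes precedence over the overlapping rows. List the sensitivity analysis in 4.3.

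If the sponsor prefers to keep the present rule as the main one, the definition line must carry the exception, the table needs an order of precedence, 4.3 needs the change and its justification, and all-cause PFS should be reported beside it.

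The cost is one row moved, a few lines of text and one further PFS run, with no new data. The main PFS result may be slightly less favourable, and the COVID-censored estimate is kept.

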6.5. EFFICACY ANALYSIS SET (PART B ONLY)

The efficacy (EFF) analysis set will contain all ITT patients who have:

- measurable disease according to RECIST v1.1 and/or GCIG criteria (Cohort 4, if applicable),
and
- a baseline tumor assessment and at least one evaluable post-baseline tumor assessment, either CT or MRI for RECIST evaluable patients, or CA-125 dosage performed after baseline, if applicable,
or
- treatment discontinuation occurred before any efficacy assessment was done due to treatment failure, defined as any: death, unacceptable toxicity, clinical deterioration and/or symptoms worsening, except those linked to COVID-19 (COVID-19 recorded as an AE in eCRF).

In order to assess these criteria, prior to each scheduled analysis where efficacy will be monitored, the study's statistician will present each of the below 7 category's data to the Debiopharm's Medical Director and IQVIA's Medical Monitor who will be tasked to adjudicate cases for exclusion from the efficacy population.

Category 1: Patients who did not have a baseline tumour assessment

- a. based on imaging or
- b. CA125 (where appropriate)

Category 2: Patients who did not have measurable disease according to

- a. RECIST or
- b. GCIC criteria (where applicable)

Category 3: Patients who did not have at least 1 post-baseline tumour assessment according to

- a. RECIST or
- b. GCIC criteria (where applicable)

Document: T:\sas\Debiopharm\Debio_1143\CZA60507\Biostatistics\Documentation\SAP\SAP Text\V5

Author: XXXXXXXXXX Version Number: 5.0
Version Date: 19APR2022

Template No.: CS_TP_BS016 Revision 5
Effective Date: 01Apr2018

Reference: CS_WI_BS005

If any of the above listed protocol deviations have been observed in categories 1 to 3, patients will be excluded from the efficacy population and will need to be “replaced”.

Category 4: Patients who discontinued study treatment before the first post-baseline tumour assessment was performed due to treatment failure, except those linked to COVID-19 (COVID-19 recorded as an Adverse Event in eCRF), which include any of the following

- a. Death
- b. Unacceptable toxicity
- c. Clinical deterioration and
- d. Symptomatic worsening

Patients who failed treatment and included in category 4, will be kept in the efficacy population and will not be replaced

Category 5: Any critical deviations that may affect the risk benefit ratio

- a. Cancer diagnosis (inclusion criteria 3 and 11)
- b. Other malignancies (exclusion criterion 13)

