17. EFFICACY OUTCOMES

17.1. PRIMARY EFFICACY

For the purposes on the analyses described below, PD could be clinical progression (as recorded on the “End of Treatment” eCRF) or radiological progression (as recorded on the “overall response – RECIST v1.1” eCRF). In case of premature discontinuation with SD at the end of study (EOS) visit, this SD will be included in the derivation of the categorical efficacy parameters only if the assessment has been performed at least 35 days after treatment start.

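### SAP 17.1 counts clinical progression on the End of Treatment form as PD, but the PFS table censors such a patient at first dose if alive with no post-baseline assessment

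*SAP*

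**What the plan says.** SAP 17.1 opens with a general rule: "For the purposes on the analyses described below, PD could be clinical progression", taken from the End of Treatment eCRF, or radiological progression, taken from the RECIST overall-response eCRF.

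SAP 17.2.1.5 defines the PFS event as the "date of the first documented disease progression or death due to any cause, whichever occurs first". Its censoring table then includes:

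- "No baseline and/or no post baseline assessment": censored at the date of first dose.
- "Treatment discontinuation for undocumented disease progression after the last adequate assessment": censored at the last adequate assessment.
- "Death before first assessment": a PFS event on the date of death. Deaths due to COVID-19 have a censoring row of their own.

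The table does not say what makes progression *documented*, or which row prevails when a patient fits more than one.

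SAP 6.5 admits to the efficacy set patients without a post-baseline assessment if "treatment discontinuation occurred before any efficacy assessment was done due to treatment failure, defined as any: death, unacceptable toxicity, clinical deterioration and/or symptoms worsening", COVID-linked cases excepted. It adds: "Patients who failed treatment and included in category 4, will be kept in the efficacy population". SAP 17.2 runs the secondary analyses on both the efficacy and the ITT/Safety sets.

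Protocol 11.4.1.1 names three PFS censoring situations: loss to follow-up, no progression by the cut-off, and new systemic therapy. It has neither a no-assessment rule nor an undocumented-progression rule. The SAP's modification history notes for version 3.0 that PFS censoring was spelled out further, but SAP 4.3, which lists departures from the protocol, does not mention these two rules. The sensitivity analyses in SAP 17.2.4 concern OS only.

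**The concern.** Kaplan-Meier estimation assumes that a censored patient has the same outlook as those still at risk. Someone who stops because the disease has worsened clinically does not. Censoring that patient at first dose takes one of the poorest outcomes out of every risk set.

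In the efficacy set this is not a rare by-product of missing data. Under SAP 6.5, a patient without a post-baseline assessment remains in that set only by having failed treatment, so the first row falls on treatment failures almost by construction. With no PFS sensitivity analysis planned, nothing in the outputs would show the effect. What is at stake is the median PFS and the PFS rates, which are secondary and descriptive.

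**Working it through.** The documents give no PFS sample size, expected median or event count, so there is no planned figure to reproduce. The check has two parts.

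**1. The rules applied to four kinds of patient**

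| Patient | SAP 17.1 | Table in 17.2.1.5 | Finding |
|---|---|---|---|
| A. Dies (not COVID-19) before any assessment | – | Fits the early-death row (event); the wording of row 1 also fits | Overlap without stated precedence; the event definition points to an event |
| B. Alive, stops for toxicity only, no scan | Not PD | Row 1: censored at first dose | No conflict with the PD definition |
| C. Alive, clinical progression on the End of Treatment form, no scan | PD | Row 1: censored at first dose | Conflict |
| D. Has a scan, then stops with clinical progression on the form and no further scan | PD | Event if the form counts as documentation; otherwise censored at the last adequate assessment | Ambiguity |

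Patient C is the substance of the point: row 1 has no exception for recorded clinical progression.

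**2. Size of the effect for patient C**

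Let k of N patients be of type C, and let S*(t) be the Kaplan-Meier curve of the other N-k. Assume nobody else is censored before the k progression dates, and take t after those dates.

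- Counted as events: S(t) = [(N-k)/N] × S*(t).
- Censored at first dose: S(t) = S*(t), because the k patients leave before any event.
- Ratio of censored to counted: N/(N-k).

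N comes from SAP 5.3: at most 15 per cohort, with futility looks at 8 and 11. k is assumed.

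- N = 15: 15/14 = 1.07 for k = 1; 15/13 = 1.15 for k = 2; 15/12 = 1.25 for k = 3; 15/11 = 1.36 for k = 4; 15/10 = 1.50 for k = 5.
- N = 11, k = 1: 11/10 = 1.10.
- N = 8, k = 1: 8/7 = 1.14.

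The smaller sizes matter because SAP 4.3 refers to the futility of the Part B cohorts.

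**Illustration, N = 15 and k = 3.** Assumptions: scans on Day 43 and every 56 days after that, evenly spaced quantiles of an exponential PFS with median 120 days for the other 12, and clinical progression on Day 28 for the three. Five of the 12 are progression-free at 6 months.

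- Clinical progression as an event: 6-month PFS 5/15 = 33.3%, median 99 days.
- Censored at first dose: 6-month PFS 5/12 = 41.7%, median 155 days. The ratio is 41.7/33.3 = 1.25, as the formula gives.
- The three die on Day 84 and the deaths are counted: 6-month PFS 33.3%, median 99 days. The inflation disappears.

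With k = 1 of 15 under the same assumptions, 6-month PFS moves from 40.0% to 42.9% and the median stays at 155 days.

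**The case against.** The strongest reply is that 17.1 and 17.2.1.5 can be read together. If clinical progression entered on the End of Treatment form is documented progression, the undocumented row covers only progression recorded nowhere, and patient D is an event. That reading is reasonable. A reader might infer that the undocumented row contradicts 17.1, but the text does not establish that; it leaves a term undefined. The reading does not rescue patient C. At best, C would also fit the row for progression documented between visits, with nothing to rank that row above row 1.

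One can also say that the 17.1 rule sits under primary efficacy and need not govern PFS. But it is addressed to the analyses below it, and 17.1.1 itself relies on derivations placed in 17.2.1, so confining it to 17.1 is strained.

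A reader might further infer that all early treatment failures leave the risk set. They do not: non-COVID deaths before the first assessment are explicit events, and stopping for toxicity alone is not progression. Nor are the death row and row 1 a true contradiction. If row 1 governed unscanned deaths, the death row would hardly ever apply. A sentence on precedence is all that is missing.

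Exposure is also limited. Protocol 8.2.1 asks for an efficacy assessment at progression or treatment discontinuation, the schedule has a scan at end of treatment, and survival is followed every 4 months, so later deaths may be counted. These reduce k without removing it: very ill patients may miss the scan, and those who start new systemic therapy are censored by another row.

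Finally, making investigator-judged progression the main event in an open-label single-arm study is a choice. Radiological PFS as the main analysis, with clinical progression in a sensitivity analysis, is also defensible. In that case 17.1 should say that its rule does not apply to PFS.

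**Conclusion.** The point holds in a limited form. As written, row 1 censors at first dose a living category 4 patient whose clinical progression is recorded and who has no scan, against the SAP's own definition of PD. This censoring is informative, and its direction is towards longer PFS.

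The factor N/(N-k) applies only to such patients, only if they are not later counted as deaths, and only with k assumed. It is not a multiplier for the undocumented row, whose patients have been scanned. The documents do not show that PFS is in fact overstated: k may be zero, and later deaths may restore the events.

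No decision rule is touched. PFS is secondary and descriptive. Confirmed ORR, on which Part B rests, is unaffected, because unscanned failures are not evaluable under SAP 17.1.2 and so are not responders. The change is still worth making, because the conflict is in the text, no planned analysis would reveal its effect, and the remedy is cheap.

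**What to change.** In SAP 17.2.1.5:

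1. Define *documented* progression consistently with 17.1, so that clinical progression on the End of Treatment form is a PFS event on its recorded date.
2. Limit row 1 to patients with no recorded clinical progression and no death.
3. State that the non-COVID early-death row takes precedence over row 1.

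In SAP 4.3, list the added censoring rules as a change from protocol 11.4.1.1. In SAP 17.2.4, add radiological-only PFS, with the current censoring, as a sensitivity analysis, and report how many patients are classified differently.

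The cost is a few lines of SAP text and one further PFS run. Some event dates will rest on investigator judgement, and PFS may look slightly less favourable. Showing both versions lets the reader see whether the choice matters.
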